STUDY PROTOCOL

Baropodometric parameters variation with body weight loss: a prospective cohort study

DATE: 11 January 2021

Scientific Background

Obesity is in one of the major public health problems of the 21st century and its prevalence has tripled in many European countries in the last decades (1). It is a strongly problem associated with a lower quality of life, as well as with the development of serious chronic metabolic, cardiac and circulatory pathologies and musculoskeletal disorders (2,3). Quantitative data showed that excessive body weight negatively effects on standing and walking (4,5).

Plantar pressure measurement is commonly used to determine specific loads on the plantar surface of the foot. There are many case studies that assess pressures of the normal foot and try to establish patterns of pathological pressures (6). The CoP represents the average of all the weight that is in contact with the surface of the floor and is expressed as the point where the vector of the vertical reaction forces of the soil is located (6,7).

In the literature it can be found how body weight influences on plantar pressure data and on the position of the CoP (8-10). Excesses of body weight has shown to have negative structural consequences in the feet and lower limbs (11-14). Obesity is also related with an anterior displacement of the CoP (15), since the instability in obese people, associated to weight increasing, seems to be determinant with CoP in an anterior position (16).

Computerized baropodometry is helpful for foot diseases diagnosis, foot function evaluation and to follow-up the treatment. It has been practiced to determine specific weight parameters in obese adults, among others (10,14). Nonetheless, there are not in the literature specific studies that have analyzed by computerized baropodometry how plantar pressures and CoP improve by decreasing body weight in obese adults.

Objective

The present research wanted to evaluate plantar pressures and antero – posterior CoP improvement by decreasing body weight in static and dynamic baropodometry data collection in obese adults.

Design

The design of the present research was based on and executed according to the STROBE reporting guideline. The study was approved by the Ethics Committee of Clinical Research of Aragón (CEICA) with number C.P.-C.I. PI17/0203. Participants voluntarily signed an informed consent. The study has been conducted in accordance with the Helsinki Principles.

Participants

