The study would include overweight subjects between 18 and 65 years old, medical weight loss indicated, no lower limb or spine pathology that might affect normal gait, nor structural or functional deformities in the feet. Candidates who not comply inclusion criteria, or reported pain in their feet within the previous 6 months, or had any previous foot surgery would be excluded. Them would be recruited at one Endocrinology and Nutrition private clinic in Huesca, Spain.

Procedure

Participants would be rigorously evaluated by the same endocrine doctor and podiatrist at baseline (Session 1) and at the end of the study after weight loss intervention (Session 2), when each participant lost between 11-12% of its corporal weight. Therefore, we will obtain 2 weight related with the two sessions: Session 1 – Weight 1; Session 2 – Weight 2.

In order to achieve the propose weight loss, lifestyle modification would be applied (17): A specific very low-calorie diet (<800kcal/day), and 2 daily sessions of 15 minutes of anaerobic physical exercise depending on the capacity of the participants (18,19).

At Session 1 and Session 2, before and after weight loss intervention, participants would be subjected to a baropodometric examination (static and dynamic). It allows to quantitatively mapping pressures in each segment of the plantar surface (20,21). For the static, participants would be asked to stand in the center of the platform for 5 seconds, with their arms on either side of the body in a natural position looking straight ahead (22). To minimize individual's corporal fluctuations in static (as body weight oscillation and imbalance) the procedure would be applied 3 times per session (22). For the dynamic, participants would be asked to walk barefoot on the platform at their normal pace following the 3-step protocol, which requires landing on the platform on the third step of gait (23). To minimize corporal individual fluctuations in dynamic (as body weight oscillation, imbalance and changes in gait speed) the procedure would be applied 3 times per session (22). Both feet would be subdivided into 9 areas: heel, midfoot, 5 MTHs, the Hallux, 2-5 toes. Selection of the areas of the present study are based in the research of Hills et al. (11), who performed a complete study of the differences of pressures between obese and non-obese subjects.

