Peak pressures of these areas in kg/cm² and the position of the CoP, were obtained using the Footwork® software (20). Peak pressure data were graphically exposed and related with the two weights for each patient.

Equipment

Participant's weight and height were measured during each session with an Año-Sayol scale and stadiometer, respectively (Año-Sayol SL, Barcelona, Spain).

Footwork® platform (AM3-IST®, France), was used for the baropodometric analysis (22, 24).

Statistical Analysis

An initial exploratory analysis of all clinical variables would be carried out. Continuous variables would be expressed as mean \pm standard deviation (SD), whereas qualitative variables would be expressed as frequencies and percentages. Continuous data would be checked for normality by Kolmogorov-Smirnov Test. Chi-Square Test would be applied to show the relationship between qualitative variables. To compare mean weights between two independent groups according to normality, Student's-T Test and ANOVA Test to "m" groups would be used. Differences between Session 1 and Session 2, would be performed using mean comparison methods, Wilcoxon when the variable does not follow normal distribution, and Student's T for related samples when there is normality. To quantify the difference between weight and plantar pressures and the CoP at Session 1 and Session 2 the "change percentage" would be calculated, which would be defined as the relative variation in percentage points between both sessions: Weight-Change % (WC%) = [(Weight at Session 2 – Weight at Session 1)/ Weight Session 1] x 100; Plantar-Pressure-Change % (PPC%) = [(Pressure at Session 2 – Pressure at Session 1)/ Pressure at Session 1] x 100; CoP-Change % = [(time CoP X+1 – time CoP X)/ time CoP X] x 100. The "change percentage" would be analyzed through Spearman correlation coefficient, according to normality.

The "improve" variable would be established in order to analyze the possible relationship between weight loss and the 9 pressure foot areas considered at Session 1

and Session 2 for both: static and dynamic baropodometry. Statistical significance level would be set at $p < 0.05$, confidence level set in the comparisons was 95%. The statistical analyses would be performed using the SPSS software 22.0 for Windows (SPSS Ibérica, Madrid, Spain).

REFERENCIAS

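### CoP-Change % divides by a position whose zero is not stated, so its size is arbitrary and, for some choices of zero, so are its ranks and sign

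*Combined protocol and SAP*

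**What the plan says.** The Objective is to "evaluate plantar pressures and antero – posterior CoP improvement by decreasing body weight", in static and dynamic recordings. The Procedure section says that peak pressures and "the position of the CoP, were obtained using the Footwork® software". The Scientific Background likewise treats the CoP as a point.

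The Statistical Analysis section introduces the change percentages with the words "To quantify the difference between weight and plantar pressures and the CoP at Session 1 and Session 2". Weight-Change % (WC%) and Plantar-Pressure-Change % (PPC%) are each written as the Session 2 value minus the Session 1 value, divided by the Session 1 value. The CoP version is "CoP-Change % = [(time CoP X+1 – time CoP X)/ time CoP X] x 100". Neither of its terms is defined, and the document gives no origin, unit or positive direction for the CoP.

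The change percentages "would be analyzed through Spearman correlation coefficient, according to normality"; the variables to be correlated are not named. Separately, "Continuous variables would be expressed as mean" with SD, and "Differences between Session 1 and Session 2, would be performed using mean comparison methods" (paired t or Wilcoxon).

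**The concern.** A percentage change has a fixed meaning only when the quantity has a natural zero. Zero kilograms and zero pressure mean the same to everyone. Zero on a position axis is wherever the software or the analyst puts it. If the zero moves, the Session 2 minus Session 1 numerator stays the same and the baseline denominator does not.

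Spearman's coefficient does not protect against this. Baselines differ between participants, so dividing by them can reorder the participants. A baseline on the far side of zero reverses that participant's sign.

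At stake are the named change index for one of the two outcomes in the Objective and the correlation that uses it.

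**Working it through.** The document gives no CoP values, so there is no figure of its own to reproduce. Every CoP number below is assumed, for illustration only.

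**1. Which reading of the formula?** The sentence that introduces it compares the CoP at the two sessions, and every description of the CoP is of a position. The likely reading is antero-posterior position at Session 2 minus position at Session 1, divided by position at Session 1. A duration is possible on the literal wording but is described nowhere else.

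**2. One participant.** Assume that the CoP lies 110 mm in front of the heel edge at Session 1 and 105 mm at Session 2. With zero placed o mm in front of the heel edge, the percentage is 100 × (105 - 110)/(110 - o).

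| Zero, o (mm) | Calculation | CoP-Change % |
|---|---|---|
| 0 (heel edge) | 100 × (-5)/110 | -4.5% |
| 50 | 100 × (-5)/60 | -8.3% |
| 90 | 100 × (-5)/20 | -25% |
| 100 | 100 × (-5)/10 | -50% |
| 110 | 100 × (-5)/0 | undefined |
| 150 | 100 × (-5)/(-40) | +12.5% |

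The difference is -5 mm in every row.

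**3. Ranks across participants.** Simulation with 400,000 draws: baseline normal with mean 110 mm and SD 10 or 15 mm; change normal with mean -5 mm and SD 5 mm, independent of baseline. The table shows the Spearman correlation of CoP-Change % with the true change in mm, and the share of backward movers whose percentage is positive.

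| Zero, o (mm) | Correlation, SD 10 / SD 15 | Backward movers shown as an increase, SD 10 / SD 15 |
|---|---|---|
| 0 | 0.99 / 0.99 | 0% / 0% |
| 50 | 0.98 / 0.96 | 0% / 0% |
| 90 | 0.82 / 0.65 | 2% / 9% |
| 100 | 0.51 / 0.36 | 16% / 25% |
| 110 | 0.00 / 0.00 | 50% / 50% |
| 150 | -0.96 / -0.90 | 100% / 99.6% |

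With zero well behind the CoP, the index keeps the order of the true shifts. With zero near the CoP it loses the order, and with zero in front of it the order reverses.

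**4. What does not matter.** Units cancel: 110 to 105 mm and 11.0 to 10.5 cm both give -4.5%. Reversing the axis about a fixed zero also cancels: 100 × (-105 + 110)/(-110) = -4.5%. A stated direction is needed only to read a result as anterior or posterior.

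**The case against.** The strongest reply is that the harm depends on a fact that the document does not give. One platform and one software package are specified, so in practice there will be one zero. If it is the heel edge, the ranks are almost untouched and only the notation needs correcting. That stands, and it limits the point.

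A reader might infer a harmful zero from the static instruction, "participants would be asked to stand in the center of the platform for 5 seconds". The document does not support that inference. The instruction concerns where to stand, says nothing about coordinates, and does not apply to the walking test.

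A reader might also infer that the correlation of CoP change with weight change will be badly distorted or reversed. This is not supported either. The Spearman partner is not named. If it is WC%, Session 2 takes place once each participant has lost 11-12% of body weight, which leaves little weight variation to correlate with. A uniform one-point window has SD 1/√12 = 0.289 points. With a change SD of 5 mm, a correlation of 0.5 would need 0.5 × 5/0.289 = 8.7 mm of CoP shift per percentage point of weight. A mean shift of 5 mm over about 11.5 points is 0.43 mm per point, which implies a correlation of about 0.43 × 0.289/5 = 0.025. There would be almost no correlation to distort.

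Finally, if the formula means a duration, that has a natural zero and the argument lapses. The term would still be undefined, and the positional objective would have no change index.

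**Conclusion.** The point holds in a conditional form. On the likely reading, CoP-Change % has an arbitrary size. Whether its ranks and sign are also unreliable depends on a zero that the document does not state: negligible at the heel edge (correlation with the true shift about 0.99), serious near or in front of the CoP (0.36 to 0.51 at 100 mm, -0.90 to -0.96 at 150 mm). These figures rest on the assumed means and SDs above.

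The defect is confined to the percentage and its Spearman analysis. A reader might infer that the whole CoP objective is compromised, but the session means and the paired comparison do not use the percentage. They remain valid if the same foot-based reference is used at both sessions. Severity is minor. Confidence is medium, because the software's origin and the intended meaning of the formula's terms are unknown.

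**What to change.** Replace the formula with: *CoP change = antero-posterior CoP position at Session 2 minus antero-posterior CoP position at Session 1, in length units (negative = backward), measured from one stated foot-based reference used at both sessions.* Calculate it separately for static and dynamic recordings. Use it in place of CoP-Change % in the Spearman analysis, and report its mean with a 95% CI beside the paired test. If a CoP timing variable is intended, define it separately.

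The cost is mainly wording, with no new visits. The percentage scale parallel to WC% and PPC% is lost. If the software output is not already foot-based it may need re-referencing, which requires stored recordings or footprints; the document does not say whether these are kept. The change does not cure the narrow weight-loss window, which would still limit any correlation with WC%.

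### If the Spearman analysis correlates pressure or CoP change with WC%, the 11-12% trigger for Session 2 leaves WC% almost constant, so those correlations can say little about weight loss

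*Combined protocol and SAP*

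**What the plan says.** All references are to the combined protocol and SAP.

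- **Procedure** times the second examination by weight loss: it takes place "when each participant lost between 11-12% of its corporal weight". Only two weights exist per participant: "Therefore, we will obtain 2 weight related with the two sessions: Session 1 – Weight 1; Session 2 – Weight 2". Each participant therefore contributes one WC%.
- **Statistical Analysis** defines WC% as (Weight 2 − Weight 1)/Weight 1 × 100, PPC% in the same form for pressure, and a CoP change: "CoP-Change % = [(time CoP X+1 – time CoP X)/ time CoP X] x 100". It then states: "The 'change percentage' would be analyzed through Spearman correlation coefficient, according to normality". No pairs are listed. Significance is set at p < 0.05.
- The same section adds: "The 'improve' variable would be established in order to analyze the possible relationship between weight loss and the 9 pressure foot areas". It does not define that variable.
- It also plans before-after tests, paired t or Wilcoxon: "Differences between Session 1 and Session 2, would be performed using mean comparison methods".
- The **Objective** concerns plantar pressures and antero-posterior "CoP improvement by decreasing body weight in static and dynamic baropodometry data collection in obese adults".
- Nothing in the plan mentions that the trigger restricts the range of WC%.

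**The concern.** A correlation with weight change can be informative only if weight change differs between participants. Here the visit rule fixes the very quantity that the correlation would use as its exposure. Ranking does not help: Spearman would order participants on differences of less than one percentage point of body weight, while the other variable carries its full measurement and biological noise.

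At stake is the interpretation. With p < 0.05 as the rule and no caveat, a non-significant coefficient could be read as evidence that pressure or CoP is unrelated to weight loss, which is the subject of the study. The design would usually produce that null even if pressure changed in proportion to weight.

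**Working it through.** **Inputs from the plan.** Trigger window 11-12%, so WC% lies between −12 and −11. One WC% per participant. Alpha 0.05 (two-sided assumed, since the plan does not say). The plan gives no sample size, slope, SD or power, so it has no figure to reproduce.

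**Step 1: spread of WC%.** This needs only the window. A uniform distribution of width w has SD = w/√12, so w = 1 gives 1/√12 = 0.289 points. The largest SD possible in a one-point range, with half the participants at each end, is 0.5. Around a mean of −11.5, the coefficient of variation is 0.289/11.5 = 2.5%, and at most 0.5/11.5 = 4.3%.

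**Step 2: expected correlation.** Assume PPC% = b × WC% + error, with residual SD s. Then r = b·SD_WC / √((b·SD_WC)² + s²). Slope b = 1 means pressure falls in proportion to weight. Assumed values are b = 1 or 3 and s = 5, 10 or 20 points. For b = 1 and w = 1:

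- s = 5: 0.289/√(0.289² + 5²) = 0.058
- s = 10: 0.029
- s = 20: 0.014

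**Step 3: sample size for 80% power.** N = 1.06 × ((1.96 + 0.842)/atanh r)² + 3. For b = 1 and w = 1 this gives 2,502, 9,990 and 39,941. For b = 3 and w = 1 (r = 0.171, 0.086, 0.043) it gives 284, 1,116 and 4,444.

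**Step 4: simulated Spearman power** at an assumed n = 50 (normal residuals, 20,000 runs). Entries are percentages for s = 5/10/20. The wider windows show what happens if achieved loss drifts beyond 11-12%.

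| Spread of WC% | Slope 1 | Slope 3 |
|---|---|---|
| 1 point, uniform | 6.8 / 5.5 / 5.2 | 20.7 / 8.5 / 5.8 |
| 1 point, maximum spread (SD 0.5) | 9.9 / 6.5 / 5.2 | 51.6 / 16.8 / 8.0 |
| 2 points, uniform | 12.4 / 6.7 / 5.6 | 62.7 / 21.2 / 8.9 |
| 3 points, uniform | 21.1 / 8.8 / 5.9 | 92.7 / 40.3 / 14.2 |
| 5 points, uniform | 48.1 / 15.8 / 7.7 | 100 / 81.1 / 30.4 |

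The Fisher z approximation for the first slope-1 row gives 6.7/5.4/5.1%, in agreement. For slope 1 and a one-point uniform window at other sizes, power is 6.2/5.3/5.0% at n = 30 and 9.0/5.6/5.0% at n = 100 (10,000 runs).

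**Step 5: spread of the coefficient.** With n = 50, b = 1, w = 1 and s = 10, 95% of simulated coefficients lie between −0.25 and 0.31, so even the sign is unreliable.

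**Step 6: the paired comparison.** As a stand-in for the planned paired test on pressures, take a one-sample t-test of a mean PPC% of −11.5 (slope 1 at the middle of the window). For s = 5/10/20, power is above 99%, above 99% and 98% at n = 50, with 95% CI half-widths of 1.4, 2.8 and 5.7 points. At n = 30 it is above 99%, above 99% and 86%.

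No calculation is made for CoP change: its slope and scale are unknown, and its formula is written in terms of a time.

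**The case against.** The strongest reply is that the harm depends on several conditions, and that the Objective does not rest on this analysis.

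- *The pairs are unstated.* True. A correlation of PPC% with CoP change would not be affected. But WC% is one of only three change percentages defined, and the plan says it wants to relate weight loss to the nine areas. If another pairing was meant, the plan still has to name it.
- *Achieved loss may drift.* The plan gives no weighing frequency or rule for overshoot, so the real spread may exceed one point. This stands as a limit: slope 3, residual SD 5 and a three-point spread would give 93% power.
- *The slope and noise are assumed.* Also true. With a residual SD of 2, slope 1 and n = 50, power is 16% in a one-point window and 82% in a three-point window. Even so, no setting tried at n = 50 reaches adequate power inside a strictly kept window; the best is 52%.
- *The test is not biased.* Correct. It keeps its 5% size, and a significant result is not invalidated. The defect is low information.
- *The before-after question is already covered.* Correct. The paired tests address it, within an uncontrolled design. The graphs are also unaffected, because weight in kg is not restricted by the trigger: "Peak pressure data were graphically exposed and related with the two weights for each patient".

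These points narrow the concern to what may be concluded from correlations with WC%. They do not remove it.

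**Conclusion.** The concern holds, on the condition that the Spearman pairs include WC%. The restriction to an SD of about 0.29 points (at most 0.5) follows from the plan's own window, provided the window is kept. How much power is lost rests on assumptions. At n = 50 with slope 1, WC% uniform over one point and residual SD 5 to 20, the test would miss a truly proportional relationship about 93-95% of the time. At slope 1, power stays at or below about 21% up to a three-point spread. It becomes adequate only with a steeper slope, lower noise or a wider achieved loss than the trigger allows.

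For CoP the same reasoning applies in direction only. If the *improve* variable is related to WC%, it carries the same restriction. The point should be fixed, because it changes what a null correlation may be taken to mean; the paired before-after conclusions are untouched. Confidence is medium, given the unlisted pairs and the assumed inputs.

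**What to change.** In Statistical Analysis:

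1. List the pairs to be correlated. Either drop those with WC% or report them descriptively: coefficient with 95% CI, alongside the observed SD and range of WC%.
2. State that the visit trigger restricts the range of WC%, so a null coefficient is not evidence of no relationship with weight loss.
3. Rest the conclusion on the paired change already planned, per foot area and for CoP, each with a 95% CI and described as the change at the weight loss achieved.
4. Define *improve*, and if it is related to WC%, attach the same caveat.

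The cost is a few sentences, with no new data, visits or tests and no change to the trigger. The downside is that no dose-response claim can be made from WC%, which this design supports poorly anyway. If achieved loss turns out to be spread over several points, the descriptive label gives up a test that might have had useful power; the reported SD and range of WC% would let readers see that.
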